## 19. INVESTIGATOR – SPONSOR COOPERATION

### 19.1 Investigator-Sponsor Agreement

A written agreement is made between the Principal Investigator, Investigation site and the Sponsor and shall be signed before start of the clinical investigation. The agreement describes the responsibility and liability for Sponsor and Investigator respectively, during the investigation.

### 19.2 Clinical Investigation Report

The Clinical Investigation Report will be prepared according to EN/ISO 14155 (6) by the Sponsor. The Sponsor has one month to finalise the Clinical Investigation Report after receipt of the final statistical report. The involved Investigators have two weeks to comment on and approve the final report. All Investigators and the Sponsor are required to sign the report. If an Investigator does not sign the final report, a justification shall be provided.

# Clinical Investigation Plan (CIP)

Study Name: VivaSight-DL study (CIS-009)  
Ethical committee number: S-20180081

CLI-000427

Rev. 02

## 19.3 Publication/Presentations

All information supplied by Ambu A/S to the Investigator in connection with this investigation shall remain the sole property of Ambu A/S and is to be considered confidential information. No confidential information shall be disclosed to others without prior written consent from Ambu A/S.

The clinical study will be registered on a public accessible database before recruitment of the first subject, e.g. <https://clinicaltrials.gov/>. A summary of the results of the investigation will be published in the same public accessible database. The subjects' identity will remain confidential.

A publication shall be prepared and submitted two months after approval (signature) of the CIR. The publication will be written by [name] from Aalborg University (first author) in cooperation with her internal supervisor at Aalborg University and Principal Investigator (last author). The Principal Investigator is responsible of pointing out any other involved investigators who should be involved in and named on the publication. The publication shall be submitted to a relevant scientific journal. Sponsor and Investigators have two weeks to comment on the draft before submission. If no comments have been received after two weeks, the submission will proceed.

If the publication has not been submitted on the agreed time plan, the Sponsor can prepare a manuscript for commercial use on the basis of the investigation or even a publication based on the study results. The Principal Investigator and other involved Investigators have the right to comment on the manuscript within two weeks. If no comments have been received after two weeks the Sponsor may proceed with the manuscript.

In the event of any disagreement in the content of a publication, the opinion of the Investigators and Ambu will be fairly represented in the publication.

The Investigators have also the right to present the results at a relevant international meeting. Sponsor and Investigators have two weeks to comment on the draft presentation. If no comments have been received after two weeks the submission will proceed.

A list of relevant conventions including deadlines for poster submissions and relevant medical journals for the final publication may be considered and written as a publication strategy.

## 20. ETHICAL CONSIDERATIONS

The clinical investigation will be conducted in accordance with The Declaration of Helsinki (8).

### 20.1 Subject information and consent

Written informed consent will be obtained from all subjects, or their legal representative, participating in the investigation after thorough written and verbal information given by the Investigator or his/her representative. Each subject will be fully informed about the aim of the investigation, procedures, potential risks or inconveniences and expected benefits. The test participants will be informed that their participation is voluntary and that they may leave the investigation at any time without giving any reason and without this having any influence on their treatment. (See appendix I).

### 20.2 Ethics Committee/Institutional Review Board (IRB)

The CIP and other relevant documents will be submitted to the appropriate Ethics Committee and their approval or written opinion will be obtained before commencement of the investigation. Any amendment to the CIP will be submitted to the same Ethics Committee.

### 20.3 Data protection

All subject data will be handled according to the Danish law for treatment of personal information, Law no. 429 of May 31, 2000 as amended by law no. 280 of April 25, 2001.

## Clinical Investigation Plan (CIP)

Study Name: VivaSight-DL study (CIS-009)  
Ethical committee number: S-20180081

CLI-000427

Rev. 02

All subject data collected during the course of this investigation will be kept strictly confidential. An investigation number will identify subjects and the monitor will have limited access to subject's files/documentation for source data verification. Any information, which could identify a subject, will remain with the Investigator where it will be filed with investigation documents. Subjects will remain anonymous for data analysis.

Should the investigation require future review, it may be necessary to allow limited access to regulatory authorities for audit purpose only.

# Clinical Investigation Plan (CIP)

Study Name: VivaSight-DL study (CIS-009)  
Ethical committee number: S-20180081

CLI-000427

Rev. 02

# Clinical Investigation Plan (CIP)

Study Name: VivaSight-DL study (CIS-009)  
 Ethical committee number: S-20180081

CLI-000427

Rev. 02

## APPENDIX V: CASE REPORT FORM

### Case Report Form – Comparison of VivaSight-DL and Conventional DLT

#### Centre Identification

Hospital name	Odense University Hospital
Department	Department V – Unit BTY
Investigators name	

#### Subject Information

Subject number:		Date of enrolment (DD-MM-YYYY)	
-----------------	--	-----------------------------------	--

#### Demographics

Sex	 Female	 Male	Height	cm
Age	years		Weight	kg
Indication			ASA Class	 I  II  III  IV

Inclusion (all questions must be answered "Yes" for the patient to be included)	Yes	No
Oral explanation of the investigation and Patient Information given		
Informed Consent obtained		
Clinical identification for single-lung ventilation during proposed surgery		
The subject is admitted to department V at OUE		
The subject is ≥ 18 years		
Exclusion (all questions must be answered "No" for the patient to be included)	Yes	No
Previously participated in the investigation		
Emergency procedure		
Known tracheobronchial anatomic anomalies		
Anticipated difficult airways		
Requiring rapid sequence induction		
Surgeries in which other lung isolation devices or techniques may be warranted (tracheostomy, nasal intubation)		
Intubation not possible using DLT (VivaSight or conventional)		
Subject requires a right-sided conventional DLT or VivaSight-DL		

Document Identification for Subject Questionnaire:

#### Physician Information

Physicians name:	
------------------	--

Inclusion (all questions must be answered "Yes" for the physician to be included)	Yes	No
Physician has with experience in < 50 DLT intubations in patients		
Physicians who has completed the simulation training course and has experienced at least 10 conventional DLT placements and three VivaSight-DLT placements in manikin		
Physician has given consent to use personal information		

Document Identification for Physician Questionnaire:

# Clinical Investigation Plan (CIP)

Study Name: VivaSight-DL study (CIS-009)  
Ethical committee number: S-20180081

CLI-000427

Rev. 02

## Case Report Form – Comparison of VivaSight-DL and Conventional DLT

### Product Information

Subject is randomized to:	 Test group (VivaSight-DL)	 Control group (Shiley)
---------------------------	--	---

Product information should only be filled out for the products being used.

Tube information	 aView monitor information (only applies for the test group)
Lot. No:	Lot. No:
Size (Fr)	 35  37  39  41

Supplementary products	Brand	Model	Additional information
Direct laryngoscope			
FOB			

### Data collection

Type of surgery	Date of surgery	Knife start (hh:mm)	Knife end (hh:mm)
 Open  Keyhole			

**Intubation** (the period from the direct laryngoscope is introduced into the subject's mouth until correct bronchial cuff placement is verified by capnography)

Bronchoscope use (n)	Repositioning prevented (n)	Tube repositioned (n)	Intubation attempts (n)	Intubation time (sec)
				sec.

Cormack-L classification	Smooth intubation?	Need to bend tube?	Resistance during tube placement?	Need of suction after tube placement?
 1  2  3  4	 Yes  No			

Bronchial cuff pressure	Tracheal cuff pressure	Comments:
Cm H 2 O	Cm H 2 O	

**Surgery** (the period from correct bronchial cuff placement is verified by capnography until the DLT exits the subject's mouth)

Bronchoscope use (n)	Repositioning prevented (n)	Tube repositioned (n)

Repositioning of tube	Time used to reposition the tube	Rate of restriction on the surgical procedure	Responsible anesthesiologist assisted	Time spend by responsible anesthesiologist
1 st repositioning	sec	 Not restricted  Restricted  Completely restricted	 Yes  No	sec
2 nd repositioning	sec	 Not restricted  Restricted  Completely restricted	 Yes  No	sec
3 rd repositioning	sec	 Not restricted  Restricted  Completely restricted	 Yes  No	sec

Extubation of the subject	Smooth extubation?	Did the subject cough?	Did the subject complain of throat pain?
	 Yes  No	 Yes  No	 Yes  No

Comments:

Any adverse events/adverse device effects?		
Yes	No	If yes: please specify (if SAE or SADE please fill out SEA or SADE form):

Any complications in relation to airway management?		
Yes	No	If yes: please specify:

Any general complications?		
Yes	No	If yes: please specify:

Any deviations from the Investigation protocol?		
Yes	No	If yes, please specify:

Were more devices than expected used (>1)?		
Yes	No	If yes, please specify why and the number of devices used:

# Clinical Investigation Plan (CIP)

Project/Product Name:  
Study name:

VivaSight-DLT  
VivaSight-DLT study

CLI-000427

38/39

Rev. 01

## APPENDIX VI: QUESTIONNAIRE FOR SUBJECTS

### Spørgeskema omhandlende helbredsrelateret livskvalitet og bivirkninger efter operation i hjerte-lunge området

I forbindelse med at De har deltaget i et forskningsstudie og har fået foretaget en operation med behov sikring af dine luftvejene på Odense universitetshospital, vil vi bede Dem besvare nedenstående spørgeskema omhandlende din generelle helbredsrelaterede livskvalitet samt eventuelle bivirkninger efter din operation.

Forsøgsperson nummer: \_\_\_\_\_

Dato for udfyldelse: \_\_\_\_\_

Tidspunkt for udfyldelse: \_\_\_\_\_

Spørgsmål omhandlende helbredsrelaterede livskvalitet						Kommentarer
Hvordan vil De vurdere Deres overordnet livskvalitet indenfor de sidste 4 uger?	 Dårlig	 Mindre god	 God	 Meget god	 Fremragende	
I hvor høj grad har De haft smerter indenfor de sidste 4 uger?	 Slet ikke	 I mindre grad	 I nogen grad	 I høj grad	 I meget høj grad	
I hvor høj grad har Deres smerter påvirket Deres hverdag?	 Slet ikke	 I mindre grad	 I nogen grad	 I høj grad	 I meget høj grad	
I hvor høj grad har De følt dem ængstelig eller deprimeret indenfor de sidste 4 uger?	 Slet ikke	 I mindre grad	 I nogen grad	 I høj grad	 I meget høj grad	
Hvordan vil De vurdere Deres helbred alt i alt?	 Dårligt	 Mindre godt	 Godt	 Meget godt	 Fremragende	
Spørgsmål omhandlende eventuelle bivirkninger efter operationen						Kommentarer
Hvor mange timer er der gået siden Deres operation?	 0-4	 5-9	 10-14	 15-19	 Over 20	
Har De tidligere fået foretaget en lignende operation?	 Ja	 Nej				
Har De oplevet hoste efter Deres operation?	 Ja	 Nej				
Hvis ja, i hvor høj grad har De hostet?	 Mild	 Moderat	 Svær			
Har De oplevet hæshed efter Deres operation?	 Ja	 Nej				
Hvis ja, i hvor høj grad har De været hæs?	 Mild	 Moderat	 Svær			
Har De haft smerter i svælget efter Deres operation?	 Ja	 Nej				
Hvis ja, hvordan vil De beskrive Deres smerter?	 Milde	 Moderate	 Svære			
Hvis spørgeskema ikke besvares, begrundes dette her:						

# Clinical Investigation Plan (CIP)

Project/Product Name: VivaSight-DLT  
Study name: VivaSight-DLT study

CLI-000427

39/39

Rev. 01

## APPENDIX VII: QUESTIONNAIRE FOR PHYSICIANS

Name of physician: \_\_\_\_\_

Date of procedure: \_\_\_\_\_

Subject number of the subject on which the procedure was performed: \_\_\_\_\_

Physician Experience						Comments
How long have you practiced medicine?	 < 1 year	 1-2 years	 2-3 years	 3-4 years	 > 4 years	
In total, how many single lumen tube placements have you performed in patients?	 0-24	 25-49	 50-74	 75-99	 ≥ 100	
Over the past three months, how many single lumen tube placements have you performed in patients?	 0-24	 25-49	 50-74	 75-99	 ≥ 100	
In total, how many conventional DLT placements have you performed in patients?	 0-9	 10-19	 20-29	 30-39	 40-49	
In total, how many VivaSight-DL placements have you performed in patients?	 0-9	 10-19	 20-29	 30-39	 40-49	

Ease of use						Comments	
Which DLT did you use for this procedure?	 VivaSight-DL	 Conventional Bronchoscopy					
How would you rate easy of insertion?	 Very difficult	 Difficult	 Acceptable	 Easy	 Very easy		
How would you rate the overall perception of quality and functionality of the DLT used?	 Very difficult	 Difficult	 Acceptable	 Easy	 Very easy		
Would you prefer to use this method for single lung ventilation in the future?	 Yes	 No	If no, please specify:

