## Tertiary end-points:

- Qualitative measures (questions to the subject) (appendix V)
  - Any side effects from the surgery
  - Daily function level prior surgery
- Qualitative measures (questions to the person who intubates) (appendix VI)
  - Ease of tube placement (very easy, easy, acceptable, difficult, very difficult)
  - How would you rate the overall perception of quality and functionality of the tube (VivaSight-DL or conventional DLT)? (Very poor, poor, acceptable, good, very good)
  - Would you prefer to use VivaSight-DL or conventional DLT in the future (VivaSight-DL/conventional DLT)

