## Tertiary end-points

- Qualitative measures (questions to the patient)
  - Any side effects from the surgery: Data will be summarized using frequency tables and examined via regression model as suitable.
  - Daily function level prior surgeryPostoperative scores will be summarized in a frequency table and examined via regression model as suitable.
- Qualitative measures (questions to the person who intubated)
  - Ease of tube placement (on a scale from 1=very easy to 5=very difficult)
  - How would you rate the overall perception of quality and functionality of the tube (DLT or VivaSight)? (Very poor, poor, acceptable, good, very good)
  - Would you prefer to use this method for single lung ventilation in the future? (yes/no)

A Chi-sqaure test will be applied to examine whether qualitative measures are significantly different for procedures using VivaSight-DLT compared to a conventional DLT.

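### The physician questionnaire prints difficulty answers under its quality and functionality question, and the plan defines the preference endpoint in two different ways

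*Combined protocol and SAP*

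**What the plan says.** Three places describe the physician-rated endpoints: the tertiary list in section 4, the tertiary part of section 18.3.3, and the form itself in Appendix VII.

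- **Quality and functionality.** Section 4 gives the answers as "Very poor, poor, acceptable, good, very good". Section 18.3.3 repeats them: "DLT or VivaSight)? (Very poor, poor, acceptable, good, very good". The form asks "How would you rate the overall perception of quality and functionality of the DLT used", but its boxes are very difficult, difficult, acceptable, easy and very easy, the same five as in the ease row above it.
- **Preference.** Section 4 has "Would you prefer to use VivaSight-DL or conventional DLT in the future (VivaSight-DL/conventional DLT". Section 18.3.3 has "Would you prefer to use this method for single lung ventilation in the future? (yes/no", and the form has "Would you prefer to use this method for single lung ventilation in the future" with yes and no boxes and a space to explain a no.
- **Ease.** Section 4 lists five words from very easy to very difficult. Section 18.3.3 adds a coding, "on a scale from 1=very easy to 5=very difficult". The form prints the same five words in the opposite order, without numbers.

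Section 7.9 has the physician complete the form immediately after surgery, about that one procedure. Section 18.3.3 plans a chi-square test between the tube groups for these items.

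**The concern.** A rating can be analysed on its defined scale only if the form offers that scale. Under the quality question it does not. A physician who thinks the tube is good has no box that says so, and must either guess which difficulty word stands nearest or leave the item blank. Different physicians may guess differently, and the form leaves no trace of how each one read it. Because the rating belongs to the moment after one procedure, asking again at the end of the study would not reliably recover it.

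The preference item has a different problem. The plan holds two definitions of the endpoint, and the form can serve only one. If the final report follows section 4, it will promise a comparison of named tubes that nobody was asked to make.

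**Working it through.** No sample size, power or error rate enters here, and the plan states no figure to reproduce. The check is a side-by-side reading of the answer options.

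| Item | Section 4 | Section 18.3.3 | Form (Appendix VII) |
|---|---|---|---|
| Quality and functionality | very poor to very good | very poor to very good | very difficult to very easy |
| Preference | VivaSight-DL or conventional DLT | yes/no on this method | yes/no on this method |
| Ease | very easy to very difficult | 1 to 5, same direction | very difficult to very easy, no codes |

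**Quality.** The defined set is {very poor, poor, acceptable, good, very good}. The printed set is {very difficult, difficult, acceptable, easy, very easy}. One word is shared, so 5 − 1 = 4 printed answers name no defined level. Even the shared word is unsafe, since a tick on acceptable among difficulty words may describe difficulty. Pairing the boxes by position (very easy with very good, and so on) would assume that an easy tube is a good tube, which is what two separate endpoints are meant to keep apart. The form contradicts both places that define the item.

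**Preference.** The two versions cannot be derived from each other:

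1. A no about the tube just used need not mean a wish for the other tube.
2. A yes can be given after a VivaSight-DL procedure and again after a conventional one.
3. The planned chi-square test changes meaning. With yes/no it compares, between arms, the willingness to use the assigned tube again. With the section 4 wording it would test whether the choice of tube depends on the arm.

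The form agrees with section 18.3.3. The conflict is therefore section 4 against the other two.

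**Ease.** All five words on the form are the five in section 4. The codes of section 18.3.3 can be assigned from the ticked word. If someone did number the boxes from left to right, a true score k would be entered as 6 − k, and applying 6 − k again restores it. The chi-square statistic, the sum of (O − E)²/E over cells, does not depend on the order of the categories.

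**Extent.** One form per procedure gives up to 25 + 25 = 50 forms in the analysed study.

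**The case against.** Much can be said for the form. On preference it collects exactly what section 18.3.3 analyses, and a yes/no about the tube just used suits a form tied to one procedure and a test between arms. A reader might infer that the questionnaire fails to measure two of the three physician endpoints. The documents do not support that count: one item contradicts both definitions, one follows the analysis section but not section 4, and one is collected as defined. Editing section 4 alone could settle the preference conflict.

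A reader might also infer that the reversed box order turns the ease result around. The form prints no codes, the words are unambiguous, and the planned test ignores order. A reversal would need a data-entry error that the plan does not contain, and recoding would cure it.

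The device question offers *Conventional Bronchoscopy* where a conventional DLT is meant. That is a slip without analytic harm: the form carries the subject number, and the CRF records the randomised group and the tube lot.

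Finally, section 7.1 pilots the procedures through section 7.9, which includes this form, in up to 10 subjects whose data are not analysed, so the fault may be noticed. That is a chance and not a safeguard. The pilot check described compares two recorders, who could agree perfectly on a form with the wrong boxes.

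None of this answers the quality item, and it remains true that no head-to-head preference is asked.

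**Conclusion.** The point stands in two parts. The quality and functionality endpoint cannot be obtained on its defined scale from the form as printed, in any of the 50 planned procedures. The preference endpoint has two definitions that are not interchangeable, and the one in section 4 is not collected.

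It would go too far to say that the quality item becomes a second ease rating. The question still asks about quality, so the answers would be ambiguous, not known to mean ease. It would also go too far to call all the physician data beyond repair. That description fits the quality ratings, and the section 4 preference if that wording is kept. It does not fit ease.

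The consequence is limited. These are tertiary measures, section 18.5 sets no pass/fail criterion for them, and section 18.7 does not list them among the effect measures of the cost-effectiveness model. The primary endpoint and the sample size are untouched. The conclusion assumes that the form in Appendix VII is the one to be used; its table reads as intact, with its own question and five boxes in each row.

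**What to change.** Before the first subject:

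1. Under the quality and functionality question, print Very poor / Poor / Acceptable / Good / Very good, as sections 4 and 18.3.3 already specify.
2. Choose one preference question and use it in section 4, section 18.3.3 and the form. If the yes/no version is kept, only section 4 needs editing. If the choice between tubes is kept, change section 18.3.3 and the form, and state what the between-arm test is meant to show.
3. As tidying, change *Conventional Bronchoscopy* to *Conventional DLT (Shiley)* and print the codes 1 to 5 of section 18.3.3 beside the ease options.

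The cost is a reprint of a one-page form and a small edit to the plan's text. No clinical procedure, sample size or primary analysis changes.
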